7. GENERAL ISSUES FOR STATISTICAL ANALYSIS

7.1 General Statistical Methodology

Descriptive summaries will be provided where appropriate for each of the primary and secondary variables. In general, tables will summarize data by treatment group that the subjects were randomized to in the prior study and visit.

All tables will be completed for the Safety Population unless otherwise specified

Continuous, quantitative, variable summaries will include the number of participants (N) with non-missing values, mean, standard deviation (SD), median, minimum, and maximum.

Categorical, qualitative, variable summaries will include the frequency and percentage of participants who are in the particular category. In general, the denominator for the percentage calculation will be based upon the total number of participants in the study population for the treatment group unless otherwise specified.

Two baselines will be utilized for most analyses: P301 baseline values are defined as the last non-missing measurement prior to the first dose of double-blind study drug in study P301; likewise, P303 baseline values are defined as the last non-missing measurement prior to the first dose of open-label study drug in study P303. Change from baseline will be defined as the post-baseline visit value minus the baseline value and will be calculated for both baselines.

ET participants will only be followed if required to monitor an on-going adverse event or other condition.

Participants are not supposed to change study sites; however, should this be necessary to allow a participant to continue in the study, participants will be analyzed under the site where they were initially enrolled.

Study day after first dose is defined as assessment date – first dose date +1. Dates prior to first dose are defined as assessment date – first dose date. Note that the protocol refers to “Day 0”; for the purposes of the datasets and analyses, this would appear as day 1.

All analyses will be performed using Statistical Analysis System (SAS[®]) Software version 9.4 or later.

Unless otherwise noted, 95% confidence intervals will be presented for statistical tests.

7.1.1 Adjustments for Multiplicity and Other Alpha Control

7.1.1.1 Multiplicity

No adjustments will be made from multiplicity and all p-values will be nominal.

7.1.2 Data Handling for Participants Who Discontinue Study Drug or Withdraw from the Study

Participants who withdraw/drop out from the study will have their ET visit data collected and included in the analysis based on the closest visit window (Week 4, 8 or 12). Visit windows will be assigned by splitting the periods between visits at the midpoint between

the visits. If more than one record falls within the window, the one closest to the target date will be used in the analysis, with preference given to the scheduled visits in the case of equidistant visits.

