9.3. Visits 3 and 4 (Weeks 4 and 8)

These visits are conducted after 4 and 8 weeks (28 ± 7 and 56 ± 7 days) of treatment respectively. The following assessments and procedures are to be conducted at each of these visits in the following general order:

- Assess for occurrence of AEs
- Perform and document an examination of the oral cavity if any oral AEs have been reported
- Assess for changes in concomitant medications
- Patient scales
 - BDI-II
- Clinician Administered Scales
 - C-SSRS
 - CGI-I considering both baselines
- Vital signs and weight
- Urine pregnancy test (for women of child-bearing potential)
- Collect returned study medication from patient
- Perform drug accountability
- Assess study drug compliance
- Dispense 2 new bottles of TNX-102 SL tablets

Review patient instructions regarding drug dosing and schedule appointment for next clinic visit.

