7.3 Safety Assessments

Safety will be assessed by:

- AE and SAEs throughout the entire duration of the study, including detailed assessment of AEs involving the oral cavity.
- Changes from both baselines in clinical laboratory test results.
- Changes from both baselines in vital signs and weight.
- Change from both baselines in BDI-II (see [Section 7.2.4](#)).
- Suicidal ideation or behavior as assessed by the C-SSRS.

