10.4 Vital Signs

Descriptive summaries (mean, SD, median, minimum, and maximum) of actual values and changes from each baseline at each assessment time point and last on-treatment assessment will be calculated for vital signs including weight, BMI, body temperature, pulse rate, systolic blood pressure and diastolic blood pressure. 95% confidence intervals will be presented for change from each baseline.

These summaries will be presented by treatment and assessment time for the Safety population. ET data will be analyzed with the closest visit that does not have a valid assessment value.

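### For BDI-II and the continuous CGI-I score, the SAP's closest-to-target rule often drops the early-termination score from the by-visit analyses, and no last-value summary recovers it

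*SAP*

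**What the plan says.** SAP 7.1.2 states that participants who withdraw "will have their ET visit data collected and included in the analysis based on the closest visit window", the windows being Weeks 4, 8 and 12. Each boundary lies halfway between neighbouring visits. On competing records the rule is: "If more than one record falls within the window, the one closest to the target date will be used in the analysis". A tie goes to the scheduled visit.

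Protocol 9.3 sets the timing of the middle visits: "These visits are conducted after 4 and 8 weeks (28 ± 7 and 56 ± 7 days) of treatment respectively". Week 12 is Day 84 ± 7 (Protocol 9.4). BDI-II and CGI-I are scored at all three visits and at ET (Protocol 9.3 to 9.5). CAPS-5, SDS and PROMIS are not scored at Weeks 4 or 8.

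SAP 7.3 lists "Change from both baselines in BDI-II" among the safety assessments. SAP 10 names BDI-II again but has no BDI-II subsection. BDI-II is modelled by MMRM on observed change at each visit, and continuous CGI-I by the same method without baseline terms (SAP 9.1.1).

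For labs and vital signs, SAP 10.2 and 10.4 use a different rule: an ET value goes to the nearest visit that still lacks a valid one. SAP 10.4 adds that "changes from each baseline at each assessment time point and last on-treatment assessment will be calculated for vital signs". The protocol synopsis (Safety Analyses) plans a descriptive BDI-II summary at endpoint. The SAP contains none under that name, and SAP 12 lists only the study-day convention as a change.

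**The concern.** SAP 7.1.2 promises that ET data are used, and its selection rule then removes many of them for the two scales with intermediate visits. The exit score is the latest information on a patient who leaves, and Protocol 9.5 asks for the ET visit preferably before a substantial lapse in medication, so many exit scores should reflect treatment. When such a score is dropped, the MMRM carries that patient's later visits implicitly from the older scheduled score, although a newer one was collected.

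Safety is the primary objective and BDI-II is one of its measures. If some patients leave because their mood has worsened, the tabulated BDI-II results could omit the scores that show it. The SAP gives no reason for handling BDI-II differently from labs and vital signs.

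**Working it through.** The documents state no figure for the share of ET scores used, so there is none to reproduce. They also give no dropout rate or timing (Protocol 12.3 and SAP 5 contain no sample-size calculation). Exit timing is therefore an assumption, and it is varied below.

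**Windows.** Targets are Days 28, 56 and 84. The midpoints are (28 + 56)/2 = 42 and (56 + 84)/2 = 70. Days 42 and 70 are placed in the earlier window unless stated.

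**One patient.** With a Week 4 visit on Day 28 and an exit on Day 38, both records fall in the Week 4 window. Their distances from target are 0 and 10 days, so the exit score is dropped.

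**Visits on target, exits uniform over Days 1-84.** Exits on Days 29-42 and 57-70 are dropped: (14 + 14)/84 = 33.3%. If Days 42 and 70 belong to the later window: (13 + 13)/84 = 31.0%.

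**Visits spread evenly over ±7 days, exits uniform.** Let the scheduled visit fall j days from target.
- For j = 0 to 7, every later exit in the window is farther from target, so 14 − j exit days are lost. The sum is 14 + 13 + ... + 7 = 84.
- For a visit k days early (k = 1 to 7), an exit is lost only from k days after target onward (ties go to the scheduled visit), so 15 − k exit days are lost. The sum is 14 + 13 + ... + 8 = 77.
- The average per window is (84 + 77)/15 = 10.73 days. Over two windows: 21.47/84 = 25.6%.
- Later exits sharing the window average 14 days, so 10.73/14 = 76.7% of the sharing exits are dropped, not all of them.

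**Systematic visit timing, exits uniform.** All visits 7 days early: 2 × 8/84 = 19.0%. All visits 7 days late: 2 × 7/84 = 16.7%.

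**Other assumed exit patterns over Days 1-84, by enumeration:**

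| Exit pattern | Visits on target | Visits spread ±7 days |
|---|---|---|
| Exit density halving every 28 days | 25.1% | 18.6% |
| Exit density halving every 14 days | 15.9% | 11.3% |
| Linearly rising | 38.8% | 30.6% |
| All before the first scheduled visit | 0% | 0% |

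The 14-day halving pattern with all visits 7 days late gives 6.6%. The spread-out patterns therefore run from roughly 7% to 39%. Among exits uniform over Days 29-84 only, the share is 50.0% with visits on target and 38.3% with ±7 days.

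**The rule in SAP 10.2 and 10.4 applied instead.** An exit sharing the Week 4 window goes to Week 8, and one sharing the Week 8 window goes to Week 12. The dropped share is 0%. With visits on target, the largest shift is 56 − 29 = 27 days, about four weeks. After a Day 21 visit and a Day 22 exit it would be 56 − 22 = 34 days.

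**The case against.** **The two sentences in SAP 7.1.2 can be read together.** Inclusion is qualified by the closest window, and the next sentences say how a record is chosen there. That is fair as a reading, but the effect remains, and so does the unexplained difference from SAP 10.2 and 10.4.

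**A reader might infer that every ET score sharing a window is lost.** The documents do not support that. Visits may be 7 days early: with a Week 4 visit on Day 21 (7 days off) and an exit on Day 30 (2 days off), the ET score is kept and the scheduled one is dropped.

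**A reader might infer that about a third of exit scores vanish from all reporting.** A third needs uniform exits and on-target visits. The scores also still appear in listings (SAP 10, Protocol 12.1), and newly emergent adverse events leading to discontinuation are tabulated (SAP 10.1.1).

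**CGI-I is mostly protected.** The listed CGI-I endpoint is the responder proportion, and SAP 9.1.2 counts missing as non-response. Only the continuous CGI-I analysis is affected.

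**Moving the ET score to the next visit re-dates it.** In the MMRM this resembles carrying a value forward and fits poorly with the stated policy of no imputation. This stands, and it limits the fix.

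**The planned endpoint summary may not be a lost safeguard.** Neither document defines endpoint for the analysis. Protocol 10.2.5 attaches the word to Visit 5, and the matching sentence in Protocol 12.1 covers only labs and vital signs. The synopsis summary would have recovered exit scores only if endpoint meant last value. This also stands, and it is a reason to define the term.

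**Consequences are limited.** All p-values are nominal, there is no formal testing order, and every patient takes the same drug.

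**Conclusion.** The point holds for BDI-II and the continuous CGI-I analysis. The selection rule often removes the ET score from the by-visit summaries and the MMRM when a scheduled Week 4 or Week 8 record shares its window. Under uniform exits the share is 31-33% with on-target visits and about 26% with ±7-day visits. Other spread-out timings give roughly 7-39%, and the share is 0% if all exits precede Week 4. These figures rest entirely on assumed timing.

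A reader might go further and infer a known favourable bias in mean BDI-II change. The documents give no basis for a size or direction: both depend on how many patients leave, when, and whether they had worsened. Nor is any effect on the difference between the two prior-treatment groups shown.

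What remains is a gap in reporting a named safety measure, which the SAP already closes for labs and vital signs. It is a cheap improvement rather than a threat to the study's conclusions.

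**What to change.** 1. Add a BDI-II subsection to SAP 10 that summarises the actual value and the change from each baseline at the last on-treatment assessment, by treatment group. Define it to include the ET score even when a scheduled record shares its window, and state how an ET score taken after a medication lapse is classified. Give continuous CGI-I the same descriptive row, without change from baseline.
2. For the BDI-II by-visit safety summary, use the ET rule of SAP 10.2 and 10.4.
3. Leave the primary MMRM specification as it is. Entering the ET score at the next empty visit should be at most a sensitivity analysis, because the score can be about four weeks early for that visit.
4. Leave the CGI-I responder analysis, with missing counted as non-response, unchanged.
5. Say in the SAP what endpoint means in the synopsis's BDI-II summary, and record any departure from it in SAP 12.

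The cost is SAP wording and one table row per scale. No data collection or study conduct changes. The one drawback is that, under item 2, some exit scores appear against a visit later than the day they were taken. The SAP already accepts this for labs and vital signs.

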7.2 Efficacy Assessments

There is no formal testing order to the efficacy assessments in this protocol; however, they are described below in approximate order of importance.

7.2.1 Clinician-Administered PTSD Scale for DSM-5 (CAPS-5)

The primary efficacy endpoint is the change from baseline in total CAPS-5 score at Week 12 (Visit 6).

The CAPS-5 is an updated and validated version of a semi-structured interview that has been designed to assess the essential features of PTSD as defined by the DSM-5 ([Weathers et al, 2013](#)). The CAPS-5 affords the clinician flexibility to inquire about symptoms and diagnostic status over different time frames, such as past week, past month, and/or worst month for lifetime. For this study, a “Diagnostic” version of the CAPS-5 (past month recall) will be utilized at the Screening visit to confirm the diagnosis of PTSD and determine eligibility. A “Symptom Severity” version of the CAPS-5 (past week recall) will be completed by the clinician at all other time points (Baseline [Visit 2] and after 12 weeks of treatment [Visits 6]).

The CAPS-5 interview contains the following components

- Life Events Checklist for DSM-5 (LEC-5): Completed by the participant at the Screening Visit (Visit 1 only)
- Criterion A – Assessment Form (CA-AF): this semi-structured interview is based on the Criterion A discussion included in the CAPS-5, but modified (by [name], CAPS-5 lead author) specifically for this study to ensure sufficient review of the traumas outlined on the participant-completed LEC-5 and to capture clear description of the participant’s index/qualifying trauma (Visit 1 only)
- PTSD symptoms, onset/duration, distress/impairment, global rating, and dissociative symptoms:
 - Criterion B: Items 1-5 (Intrusion symptoms)
 - Criterion C: Items 6-7 (Avoidance symptoms)
 - Criterion D: Items 8-14 (Negative alterations in cognitions & mood)
 - Criterion E: Items 15-20 (Arousal and reactivity symptoms)
 - Criterion F: Items 21-22 (Onset and duration of symptoms)
 - Criterion G: Items 23-25 (Distress and impairment due to PTSD)
 - Global ratings: Items 26-27 (Validity, severity)
 - Dissociative symptoms: Items 29 (Depersonalization) and 30 (Derealization)

In addition to the total symptom score (obtained from the sum of Criteria B-E), the CAPS-5 affords the opportunity to examine clusters of symptoms, including Criterion B

(intrusion symptoms), Criterion C (persistent avoidance), Criterion D (negative cognitions and mood), and Criterion E (arousal and reactivity), all of which will be secondary efficacy endpoints.

In the case of CAPS-5 items that are not resolvable at the site level (via query, review of source), the following conventions will be employed for handling of missing CAPS-5 items:

- For ≤ 2 missing item scores in Criterion B, D, or E, the average of the other items within the criterion will be used for the missing item;
- For < 2 missing items scores in Criterion C, which only has 2 items, the value of the non-missing items will be used for the missing item;
- For > 2 missing items in Criterion B, D, or E, or > 1 missing item in the Criterion C, the total CAPS-5 score will be considered missing overall.

7.2.2 Clinician Global Impression of Improvement (CGI-I)

The CGI-I will be completed by an Investigator to evaluate the participant's status since initiation of treatment. The CGI-I, status since initiation of treatment, is the first key secondary efficacy endpoint in this study. The CGI-I should be completed toward the end of each in-clinic post-Baseline study visit once all other assessments are available for the investigator's review. Once the participant has been randomized, an Investigator completes the CGI-I assessment after 4, 8, and 12 weeks of treatment in order to assess the overall change in the participant's status and answer the following question:

Since the initiation of treatment at Visit 2, the participant is:

- 1 = Very much improved
- 2 = Much improved
- 3 = Minimally improved
- 4 = No change
- 5 = Minimally worse
- 6 = Much worse
- 7 = Very much worse

The key secondary analysis of CGI will treat it as a continuous variable (scored 1-7 as above). There will be an additional outcome presented where a responder on the CGI-I is defined a participant who is scored as 'Very much improved' or 'Much improved' and compared between the study arms.

7.2.3 Sheehan Disability Scale (SDS)

The SDS scale is a self-report questionnaire that was designed to assess the participant's view of the degree to which symptoms have disrupted work/school, social life/leisure activities, and family life/home responsibilities during the previous two weeks ([Sheehan & Sheehan, 2008](#)). In addition, the SDS asks the participant to provide the number of days of work/school lost as well as unproductive days in the past two weeks. The SDS scale will be completed by the participant at Baseline and after 12 weeks of treatment (Visits 6). A total score will be calculated summing the three individual 11-point (0-10)

scales. For participants that do not respond to the work/school disruption because the participant checked the box indicating he/she has not worked or attended school for reasons unrelated to the disorder (PTSD), the total score will sum the other two domain questions and multiply by 1.5 (rounding up to the nearest whole number) to maintain the scale of 0-30 for the total score. Participants with missing values on the other items will be missing for the total.

7.2.4 Other Efficacy Outcomes

7.2.4.1 PROMIS Sleep Disturbance Instrument

PROMIS refers to the Patient-Reported Outcome Measurement Information System (www.nihpromis.org), a National Institutes of Health (NIH)-funded initiative to develop instruments to be used across chronic conditions.

The PROMIS sleep disturbance scale (short form 8a) will be assessed at Baseline and after 12 weeks of treatment (Visits 6).

The sleep disturbance scale will be calculated summing the individual item scores of the 8 items. These summed scores will be transformed to T-scores using the published conversions (see [Section 14.2](#)).

7.2.4.2 BDI-II

The Beck Depression Inventory (BDI-II) is a 21-item measure of the severity of current depressive symptoms, extensively validated for use in both medical and mental health populations. While this instrument does not provide a psychiatric diagnosis of depression and has considerable overlap with PTSD associated symptoms, it does provide a continuous scale for measuring changes in the severity of symptomatology. The BDI-II will be completed by the participant at all visits.

7.3 Safety Assessments

Safety will be assessed by:

- AE and SAEs throughout the entire duration of the study, including detailed assessment of AEs involving the oral cavity.
- Changes from both baselines in clinical laboratory test results.
- Changes from both baselines in vital signs and weight.
- Change from both baselines in BDI-II (see [Section 7.2.4](#)).
- Suicidal ideation or behavior as assessed by the C-SSRS.

7.3.1 Adverse Event and Prior/Concomitant Medication handling conventions

To handle missing or partial AE and prior/concomitant medication dates, the following rules will be applied.

For partial start dates:

1. If the year is unknown, then do not impute the date but assign a missing value.
2. If the month is unknown, then:
 - a. If the year matches the year of the first dose date, then impute the month and day of the first dose date.
 - b. Otherwise, assign “January.”
3. If the day is unknown, then:
 - a. If the month and year match the month and year of the first dose date, then impute the day of the first dose date.
 - b. Otherwise, assign “01.”

For partial end dates:

1. If the year is unknown, then do not impute the date but assign a missing value.
2. If the month is unknown, then assign “December.”
3. If the day is unknown, then assign the last day of the month.

After implementing the rules above, to determine whether medications with missing start or stop dates are prior or concomitant medications, the following strategy will be used:

1. If the start date and stop date are both missing, then the most conservative approach is taken and the medication is considered to be a concomitant medication.
2. If the start date is missing but the stop date is not missing and is after the day of first study dose administration, then the most conservative approach is taken and the medication is considered to be concomitant.
3. If the start date is missing but the stop date is not missing and is on or before the day of first study dose and after the date of signed informed consent, then the medication is considered to be a prior medication.
4. If the start date is not missing but the stop date is missing, then the most conservative approach is taken and medication is considered to be concomitant.

The missing severity of an AE will be imputed to “severe”; the missing relationship to study drug of an AE will be imputed to “related”.

8. STUDY PARTICIPANTS AND DEMOGRAPHICS

8.1 Disposition of Participants and Withdrawals

The numbers and percentage of participants entering, completing the study, and withdrawing from the study, along with reasons for withdrawal, will be tabulated overall and by treatment group. This summary will be based on all participants who have data entered into the database.

8.2 Protocol Deviations

Protocol deviations will be checked on complete data for all participants, determined during a data review meeting before database lock and the final analysis.

Protocol deviations will be summarized by type and by treatment group for the Safety population. Protocol “violations” are not differentiated from deviations; instead, each deviation is identified either as “major” or “minor” depending upon its potential impact upon the integrity of the study data or the participant’s well-being.

Individual participants with protocol deviations will be listed.

8.3 Demographics and Other Baseline Characteristics

Descriptive summaries of the demographic and other baseline characteristics will be completed for all participants in the safety population by treatment groups, unless otherwise specified.

Descriptive summaries of demographic and other baseline conditions will include:

- Demographics (age, gender, race/ethnicity, height, weight, body mass index (BMI), family status, education, presence of current MDE, current nicotine, alcohol and THC usage, and employment status). In addition to the safety population, these will also be repeated for all randomized participants and the mITT population.
- CAPS-5 Assessment (Diagnostic version)

Other assessment’s baseline values will be reported with their respective follow-up measures.

Medical History will be coded using Medical Dictionary for Regulatory Activities (MedDRA) version 19.0 and summarized by System Organ Class (SOC) and Preferred Term using frequency counts by treatment group. Note that the medical history is collected in the lead-in study; this analysis displays that information for the population of subjects that entered this study.

